### **10.2 Sample size calculation**

It is planned to recruit 20 patients to RehaClinic Kilchberg. This results in 10 patients each for the experimental group and the control group. This number is based more on the temporal than on the statistical factor. It serves only for the descriptive statistics in order to be able to make already first assumptions and to be able to carry out a SampleSize calculation. If this number is not reached by the end of April, the pilot study will nevertheless end. This should ensure the writing of the master thesis, so that it can be delivered on time.

### **10.3 plannend analysis**

For the pilot study mainly the BIAS (systemic errors) should be analyzed.

These could turn out to be selective or during the test procedure. But of course also in the amount of data collected.

The collected records are also discussed.

#### **10.3.1 Analysis of datasets and study groups**

The walking speed and fall risk of stroke patients during inpatient rehabilitation is analyzed. All data is logged and merged into a table. The records are encrypted to preserve the anonymity of the patients.

### **10.3.2 Primary analysis**

The analysis will be carried out by the investigator after completion of the entire intervention.

### **10.3.3 Safety analysis**

The physiotherapists will be trained by the examiner in the assessments and the balance training before starting the pilot study.

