### **4.4 Safety goals**

A safety goal is the fall prophylaxis. The safety is to be ensured by the bar, on which the patients can hold on, if they lose the balance. In addition, the patients should as far as possible achieve a walking speed with which they can safely cross a street.

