### **5.3 Safety targets**

The risk of falling should be reduced. In order to be able to prove this, patients should achieve a score of at least 45 in the reassessment of the BBS. In addition, a walking speed of 0.8 m/sec in a 10m walk test should be achieved.

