### Falling risk

The Berg Balance Scale is used to determine the risk of falling. The BBS detects deficits at both activity and body function levels. It consists of 14 items. Scaling takes place from 0 points (not possible) to 4 points (independently possible). This results in a total score of 56 points. The individual items are shown in the template in the appendix.

Very good intertester reliability was found in a study of 112 stroke patients (Mao, Hsueh, Tang, Sheu, & Hsieh, 2002).

The best values in terms of validity resulted from the combination of the BBS with the walking speed. This gave a specificity of 70% and 91% sensitivity (Schädler, et al., 2012).

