## **8.2.3 Recording safety targets**

### **8.2.3.1 Serious Adverse Event (SAE)**

A SAE would be a fall of the patient. If this has happened, a fall protocol will be created on the RehaClinic intranet. It records how the fall came about and under what circumstances, when the fall took place, and which people were present. The patient is examined by the ward physician and, where appropriate, measures for further examination or treatment are initiated. If the patient later describes the fall, as unobserved, the same procedure nevertheless takes place.

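### Section 10.3.3 plans no safety analysis, and 5.3 accepts two test scores as proof of lower fall risk although falls are recorded; no count of falls by arm is planned

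*Combined protocol and SAP*

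**What the plan says.** Section 4.4 sets the aim: "A safety goal is the fall prophylaxis". Section 5.3 turns it into a target, "The risk of falling should be reduced", and says how the target is to be shown: "In order to be able to prove this, patients should achieve a score of at least 45 in the reassessment of the BBS". It then adds a second criterion: "In addition, a walking speed of 0.8 m/sec in a 10m walk test should be achieved". Observed falls are not a criterion.

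Falls are nevertheless collected. Section 8.2.3.1 says "A SAE would be a fall of the patient", and then "If this has happened, a fall protocol will be created on the RehaClinic intranet". That record covers how, when and in whose presence the patient fell, and the same procedure applies to an unobserved fall that the patient reports later. The section does not limit this to one arm, so I read it as applying to both.

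The whole of 10.3.3 is the sentence "The physiotherapists will be trained by the examiner in the assessments and the balance training before starting the pilot study".

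**The concern.** The plan names an event as its safety goal, records that event, and then assesses the goal by test scores alone. The section where the event should be analysed holds a statement about training staff. A patient who falls twice during the three weeks and then scores 46 points at 0.8 m/s meets both criteria in 5.3, and nothing in the statistical chapter would bring the two falls into the results.

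The stake is the comparison of settings. Both arms do the same exercises, including eyes-closed and unstable-surface work (7.5.1, 7.5.2). They differ in whether the patient trains alone or in a group of 3 to 6. Section 3 itself argues that the individual setting brings less distraction and individual instruction, and 3.6 discusses the risk of falling. Falls by arm are therefore an obvious safety outcome for this trial and for the larger trial it is meant to prepare (4.1).

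**Working it through.** **Step 1: is a fall count planned anywhere else?**
- Section 10 lists means, standard deviations, absolute and relative frequencies and an odds ratio. It assigns none of them to falls.
- Section 10.3.1 analyses walking speed and fall risk. Under 8.2 (Falling risk), fall risk is determined by the BBS, so this is a score and not an event.
- Sections 9.2 and 9.3 require individual documentation and causality assessment of SAEs, and reporting to the ethics committee where a link to the intervention cannot be ruled out.
- The annual safety report lists SAEs in summary and states no split by arm.

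None of these is a comparison of falls between arms.

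**Step 2: would the SAE route capture every fall?** Section 8.2.3.1 calls a fall an SAE. Section 9.1 defines an SAE by unplanned or extended inpatient treatment, permanent or severe disability, threat to life or death, or congenital anomaly. A fall alone meets none of these. A fall without serious consequences might therefore be on the intranet record but not in the SAE listing.

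**Step 3: which patients would be counted?** Section 10.4 excludes a patient whose data cannot be completed, and 7.4 replaces withdrawn patients where possible. Sections 7.4 and 7.8 try to obtain a reassessment, but a patient who stops after a fall and is not reassessed would be missing from the scores on which 5.3 relies. The data are archived, so the fall could still be counted if the plan asked for it.

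**Step 4: how many fallers might there be?** The plan gives no fall rate for its own setting and period, and its sample size of 10 + 10 = 20 was set by time (10.2), so there is no planned figure to reproduce. Fallers expected = rate x 20:
- 5% (assumed): 0.05 x 20 = 1
- 10% (assumed): 0.10 x 20 = 2
- 39% (section 3, no observation period given): 0.39 x 20 = 7.8

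**Step 5: what could a table by arm show with 10 per arm?**
- Exact 95% upper limit for 0 of 10: 1 - 0.025^(1/10) = 30.8%. For 3 of 10 the exact limits are 6.7% to 65.2%.
- Two-sided Fisher p: 0.21 for 3 against 0, 0.14 for 5 against 1, 0.033 for 5 against 0.
- Power to detect true proportions of 40% against 20% (assumed): about 6%.
- With equal true rates, the chance that the arms show unequal numbers of fallers is 1 - P(tie): 1 - 0.463 = 54% at 5%, 1 - 0.313 = 69% at 10%, 1 - 0.181 = 82% at 39%.

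A table would describe. It would not test.

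**The case against.** The best defence is that falls are not outside the safety framework. Section 8.2.3.1 sits under the recording of safety targets, SAEs are documented, assessed for causality and listed, and 2.7 allows the trial to stop if safety is in doubt. The records and the allocation are both kept (12.1.2), so a table could be made later. This is a 20-patient pilot for feasibility and sample size, and 10.2 limits it to description. All of that stands. It narrows the gap to the missing analysis and the wording of 5.3, but it does not fill the gap.

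Several stronger readings are tempting, and the documents do not support them:
- **That the plan would declare success in an arm where more patients fell.** Section 5.3 sets targets for patients and never mentions arms. Such a conclusion is possible but is not a stated rule.
- **That falls during training contradict a good final score.** They happen before the reassessment. They measure harm during the study, which is a separate question. With no baseline period, they cannot show a reduction either.
- **That the scores are shown to predict falls poorly.** Section 8.2 reports "This gave a specificity of 70% and 91% sensitivity" for BBS plus walking speed, but gives no cut-offs and does not say that falls were the criterion. If the figures are assumed to apply, the relevant quantity is the share of patients passing the scores who still fall: 0.39 x 0.09 / (0.39 x 0.09 + 0.61 x 0.70) = 0.0351 / 0.4621 = 7.6%. That is not zero, but it is no strong indictment. How often patients who fail the scores fall is beside the point.
- **That group patients are less closely supervised.** No section states how many therapists attend a group session, and the safeguards (bar, protective step, opening the eyes) are not limited to one arm.
- **That about 8 patients will fall.** The 39% has no stated observation period and may not fit three weeks.

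**Conclusion.** The point holds in a limited form. Section 10.3.3 specifies no safety analysis, 5.3 treats two scores as proof of lower fall risk, and no section plans a comparison of recorded falls by arm. The trial's safety conclusion could therefore ignore a difference in falls, and patients with incomplete data could drop out of the scores as well. The expected number of fallers is unknown, from about 1 to about 8 of 20 over the range shown. The primary result is unaffected. The conclusion rests on reading 8.2.3.1 as covering both arms; the figures in steps 4 and 5 are illustrations under assumed rates.

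**What to change.** Replace the text of 10.3.3 with a descriptive analysis along these lines: *For all randomised patients, by arm, including those withdrawn, replaced or with incomplete data, from consent to reassessment (or last observation if there is none): number of patients with at least one fall, number of falls, and falls per patient-week, each split into during and outside balance sessions. All falls are counted, whatever their SAE status.* Starting at consent matches section 9. Drawing on the fall protocols, and not only on the SAE pages, keeps falls without serious consequences in the count.

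In 5.3, name observed falls by arm as a safety outcome, and describe BBS and walking speed as supportive measures of fall risk and not as proof of reduction. Reconcile 8.2.3.1 with the SAE definition in 9.1.

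The cost is a few sentences and one table, built from fall protocols already required and linked to the allocation. The change touches the target criteria and the statistical evaluation, so under 2.8 it needs ethics committee approval. The limit to accept is imprecision: with 10 per arm the counts should be reported without a test, and they cannot show a reduction from baseline.

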### **10.3.4 Deviations from the original statistics plan**

Should changes occur, the EC will be informed in writing and the decision substantiated.

## **10.4 Dealing with missing data and drop-outs**

If the data can not be completed, the patient is excluded so as to avoid falsification of the results. The existing data and also the drop-outs will be archived anyway.

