## **7.1 Eligibility criteria**

### **7.1.1 Inclusion criteria**

Patients who meet all of the following inclusion criteria may be included in the clinical trial.

- min. 18 years
- stroke starting from Rehaphase B
- ability to understand therapy instructions
- walkable with aids

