### Walking speed

The walking speed is measured using the 10m walk test. This has a high reliability for stroke patients (Flansbjerg, Holback, Downham, Patten, & Lexell, 2005).

The patient walks a distance of 20m. The start and end points are each marked with a cone. The patient is asked to walk this route as fast as possible, but so that he feels safe. The measurement begins as soon as one of the lower extremities crosses the 5m mark and stops when one of the lower extremities crosses the 15m mark. The therapist goes with the patient to see this. This is to exclude the startup and stopping delays (Schädler, et al., 2012). Three consecutive passes are taken to calculate the mean.

This gives you the walking speed in m / sec if you calculate 10m divided by the seconds. If an aid was needed to go, this will be noted.

This test has high reliability with an ICC of 0.94-0.97 (Flansbjerg, Holback, Downham, Patten, & Lexell, 2005).

In addition, stroke abilities were classified as having everyday abilities (Perry, Garrett, Gronley, & Mulroy, 1995).

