## **10 STATISTICS**

One aim of this pilot study is to determine an appropriate number of cases. Therefore, with the obtained data set using G \* Power Ver. 3.1.9.2 the SampleSize is calculated.

Further descriptive statistics are done with SPSS version 25. The mean values for each assessment are calculated. The absolute and relative frequencies are calculated. To determine the scattering parameters, the standard deviation is determined.

To determine if there is a difference between intervention and control group, first the odds ratio is shown.

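### A patient present at reassessment but unable to walk the timed distance has no defined speed and is excluded, so loss of walking drops out of the arm mean and the SD

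*Combined protocol and SAP*

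**What the plan says.** The Walking speed part of section 8.2 describes a timed middle 10 m of a 20 m walk and converts time to speed: "This gives you the walking speed in m / sec if you calculate 10m divided by the seconds". It adds: "Three consecutive passes are taken to calculate the mean". It does not say what is recorded when no pass can be completed.

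Section 7.1.1 requires patients to be "walkable with aids" at entry. Section 8.1 schedules the walk test, BBS and FAC on the day after the sixth session. After an early stop, section 7.8 asks for the walk test and BBS on the next treatment day unless the patient has been relocated. Section 7.4 adds that a patient who stops early is replaced if possible.

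Section 10.4 handles incomplete data in one sentence: "If the data can not be completed, the patient is excluded so as to avoid falsification of the results". It goes on to say that existing data and drop-outs are archived. It does not separate inability to perform the test from other reasons for a missing value.

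Section 10 summarises what remains: "The mean values for each assessment are calculated", and "To determine the scattering parameters, the standard deviation is determined". The same data set feeds the sample size calculation for the follow-up trial. Section 10.2 gives the arm size: "This results in 10 patients each for the experimental group and the control group".

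**The concern.** Everyone enrolled can walk, if necessary with aids. Someone who attends reassessment and cannot cover the distance has therefore deteriorated on the primary outcome. The speed formula needs a time, and this patient has none. The data cannot be completed, and section 10.4 removes the whole patient, not only the missing variable. BBS and FAC can still be scored in a non-walker, and FAC is the measure that would show the loss, but these values leave the analysis too.

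A patient who walks very slowly stays in and lowers the arm mean, while one who declines further, to not walking at all, is removed and the mean rises. With ten patients per arm, one case is enough to show. It touches both purposes of the pilot: the comparison of individual with group training, and the SD passed to the follow-up sample size.

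The protocol treats falls as a foreseeable risk. Section 8.2.3.1 states: "A SAE would be a fall of the patient", and sections 3 and 3.1 cite falls in 39% and about 46% of stroke patients. It gives no figure for falls, or anything else, that end walking.

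**Working it through.** **Plan's own figure.** 10 + 10 = 20 patients. Section 10.2 says the number was set mainly by time, and no alpha, power, SD or dropout rate is stated. There is nothing further to reproduce, and no stated figure is contradicted.

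**Inputs.** From the documents: 10 per arm (10.2) and 0.18 m/s as a successful improvement (5.1). Assumed, because the documents give no values: one non-walker in an arm; the nine walkers gain 0.18 m/s on average; SD of their change 0.20 m/s; non-walker's baseline 0.4, 0.6 or 0.8 m/s; two-sided alpha 0.05 and 80% power for the follow-up trial.

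**Step 1: mean change.** With the non-walker scored 0 at the end, that patient's change is minus the baseline *b*:

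mean change = (9 × 0.18 − *b*) / 10

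| *b* (m/s) | Scored 0 | Excluded | Shift | Shift / 0.18 |
|---|---|---|---|---|
| 0.4 | (1.62 − 0.4)/10 = 0.122 | 0.18 | 0.058 | 32% |
| 0.6 | (1.62 − 0.6)/10 = 0.102 | 0.18 | 0.078 | 43% |
| 0.8 | (1.62 − 0.8)/10 = 0.082 | 0.18 | 0.098 | 54% |

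**Step 2: mean speed at reassessment.** Section 10 plans means for each assessment, so the end value matters too. If the walkers' mean is *m*, the arm mean is *m* with exclusion and 0.9*m* with the zero. For *m* of 0.4 to 1.0 m/s (assumed), exclusion raises the arm mean by 0.04 to 0.10 m/s.

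**Step 3: SD of change.** Let *D* = 0.18 + *b* be the gap between the walkers' mean change and the non-walker's change. Adding one value to nine gives

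variance = (8 × 0.20² + 0.9 × *D*²) / 9

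- *b* = 0.4: (0.32 + 0.9 × 0.58²)/9 = 0.0692, SD 0.263
- *b* = 0.6: (0.32 + 0.9 × 0.78²)/9 = 0.0964, SD 0.310
- *b* = 0.8: (0.32 + 0.9 × 0.98²)/9 = 0.1316, SD 0.363

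The zero raises the SD whenever 0.9*D*² exceeds 0.20², that is when *D* is above 0.21 m/s. That holds at all three baselines, but it is not a mathematical necessity.

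**Step 4: follow-up sample size.** n per arm = 2 × (1.96 + 0.84)² × variance / 0.18², which is about 484.5 × variance, rounded up.

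- Exclusion, SD 0.20: 484.5 × 0.04 = 19.4, so 20 per arm.
- Affected arm's SD used for both arms: 34, 47 and 64 per arm at *b* = 0.4, 0.6 and 0.8.
- Variance averaged with an unaffected arm of SD 0.20, for example (0.0692 + 0.04)/2 = 0.0546 at *b* = 0.4: 27, 34 and 42 per arm.

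**Step 5: difference between arms.** Let walkers in both arms gain 0.18, so exclusion always shows a difference of 0. At *b* = 0.4, individual minus group training becomes −0.058 m/s with the non-walker scored 0 in the individual arm, +0.058 m/s with that patient in the group arm, and 0 with one such patient in each arm. The direction depends on where the loss occurs.

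**The case against.** **The exclusion is inferred.** Section 10.4 never mentions inability to walk. That stands as a caution. Still, its wording is general, has no exception, and leads to exclusion without added assumptions.

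**The case may not arise.** Nothing suggests patients lose walking within three weeks, aids are allowed in the test, and training takes place near a bar. A patient with an injurious fall or a new deficit may be relocated and would stay missing under any sensible rule. This stands. What is left is the patient still in the clinic, and the frequency may be zero.

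**Zero is a convention.** A reader might infer that such a patient's speed simply is 0 m/s and that any other handling is wrong. The documents neither adopt nor reject that score. Reporting inability separately or using a rank-based summary are alternatives. What can be criticised is the automatic exclusion, not the absence of this particular value.

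**The direction is not fixed.** A reader might also infer that the rule favours individual training. Step 5 shows otherwise: a non-walker lost from the group arm flatters the control and works against the study's hypothesis.

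**A zero brings its own problem.** As steps 3 and 4 show, one zero among ten can dominate the SD. This stands, and is why results are needed both ways.

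**The record survives.** Drop-outs are archived, reasons for early withdrawal are source data (12.1.2), and section 10.3 makes bias the main analysis. None of this returns the patient to the comparison or requires counts by arm.

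**Conclusion.** The point holds in a limited form. Sections 8.2, 10.4 and 10 together remove a patient because of the primary outcome when that patient attends reassessment but physically cannot complete a timed pass. Measured against a score of 0, the affected arm's mean speed is overstated in every such case, and its SD will usually be understated. With equal gains among the walkers, the between-arm difference is biased only when non-walkers differ between arms in number or baseline, and then in either direction. With ten per arm, a single case creates that imbalance.

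One such patient moves the arm's mean gain by 0.06 to 0.10 m/s, about a third to a half of the 0.18 m/s named in section 5.1. That yardstick is a within-patient improvement, not a planned difference between arms. The baselines, gain, SD and number of non-walkers are all assumptions, so these sizes illustrate what could happen and predict nothing.

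The study is a descriptive pilot that claims no firm inference, so the point is minor to moderate. It should be settled before the data are seen, because there is no blinding (6.5) and the investigator performs the analysis (10.3.2).

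**What to change.** In section 8.2, add that a patient present at reassessment who physically cannot complete any timed 10 m pass is scored 0 m/s by convention, with the reason on the CRF. Add a separate sentence on how one or two completed passes are averaged, so that the zero is not used for them.

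In section 10.4, add that these patients stay in the comparison with their BBS and FAC values. Patients who are relocated, absent or refuse remain missing and are counted by arm with reasons.

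In section 10, report the arm means, SDs and resulting sample size both with and without the 0 m/s values.

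The cost is a few sentences, one CRF tick box with a reason, and one repeated summary. No treatment, visit or test changes. The drawback is that a zero is an outlier that can inflate the SD, and showing both results makes that visible.

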## **11 SUITABILITY TEST CENTER**

The RehaClinic Kilchberg is a neurological rehabilitation facility with phases B-D. Between February and the end of March 2018, 78% of patients were 71% stroke patients. It is integrated in the Seepital Kilchberg.

The patients stay stationary between four weeks and about 5 months (with early rehabilitation).

RehaClinic AG has its own research department, which receives awards at regular intervals.

There are no other studies taking place at the same time in the RehaClinic Kilchberg.

## **12 QUALITY ASSURANCE AND CONTROL**

The sponsor examiner is responsible for implementing and maintaining a quality system with written SOPs and Working Instructions (WI). This ensures that the clinical trial and trial data are treated according to protocol, GCP and valid law.

### **12.1 DOCUMENTATION AND STORAGE OF THE DATA**

The clinical trial is strictly conducted according to the protocol. If changes are necessary, they must be recorded in a protocol amendment. All inspection plan changes must be signed by the sponsor investigator and submitted to the competent ethics committee for approval.

